5.3.2.1 Study Drug Compliance

Participants in cohorts 1 and 2 will be expected to dose once daily with 2 capsules per dose (2 capsules per day); in cohort 3 – twice daily with 1 capsule (2 capsules per day).

Compliance will be calculated across the whole treatment period.

Compliance calculation will be based on the daily diary and drug accountability data.

Expected capsules

Expected capsules for the treatment period will be calculated as:

$$\text{Expected capsules} = 2 * (\text{End date of treatment period} - \text{Start date of treatment period} + 1).$$

End date of treatment period = Date of the last dose of study drug.

Start date of treatment period = Day 1.

Actual capsules taken

Actual capsules taken will be calculated from the dosing diary using entries between the start and end days inclusively and drug accountability data.

Dosing diary number of capsules definitely not taken will be calculated as:

Number of capsules not taken from dosing diary days where participant specifically chose the answer 'did not take dose' or 'took some of dose'.

Drug accountability number of capsules definitely not taken will be calculated as:

Expected capsules – (Number of capsules dispensed* – Number of capsules returned*)

* Through the whole treatment period.

Actual capsules taken will be then calculated as:

Actual capsules taken = Expected capsules – max(Dosing diary number of capsules definitely not taken, Drug accountability number of capsules definitely not taken)

Study drug compliance

Study drug compliance will be calculated as:

Study drug compliance (%) = $100 \times \text{Actual capsules taken} / \text{Expected capsules taken}$.

Study drug compliance will also be categorised as:

- <75%
- ≥75%

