6.2. Investigational Medicinal Product(s) to be Administered

The study IMP (EDP1815 or placebo) will be administered as capsules for 16 weeks in total.

Study IMP is to be taken with water at approximately the same times each day (± 2 hours, whenever possible). With twice daily dosing, administration should be in the morning and evening, with the doses separated by approximately 12 hours (± 2 hours, whenever possible).

Participants should refrain from consuming acidic drinks (such as cola/soda, coffee, sports and energy drinks, flavored waters and citrus juices) 1 hour either side of dosing and from eating 2 hours before and 1 hour after dosing.

Table 6-1: IMP to be Administered

Cohort	Formulation	Capsule Number and Frequency	Total Daily Dose / Total Daily Cell Count	Route	Storage Conditions (per label)
1	8.0x10 ¹⁰ cells/enteric coated capsule (EC1)	2 capsules, once daily	1.6x10 ¹¹ cells	Oral	Store 2 to 8°C
2	3.2x10 ¹¹ cells/enteric coated capsule (EC1)	2 capsules, once daily	6.4x10 ¹¹ cells	Oral	Store 2 to 8°C
3	3.2x10 ¹¹ cells/enteric coated capsule (EC1)	1 capsule, twice daily	6.4 x10 ¹¹ cells	Oral	Store 2 to 8°C
4	8.0x10 ¹⁰ cells/enteric coated capsule (EC2)	1 capsule, once daily	8.0x10 ¹⁰ cells	Oral	Store 2 to 8°C

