5.1 General Study Design and Plan

This is a randomised, double-blind, placebo-controlled study to evaluate the efficacy, safety and tolerability of EDP1815 as compared to placebo in participants with mild, moderate and severe atopic dermatitis.

Cohorts 1, 2 & 3 will be run concurrently, and Cohort 4 recruitment will commence after enrollment for Cohorts 1, 2, & 3 are completed. During the Cohorts 1, 2, & 3 enrolment after eligibility is confirmed during the screening period ([Protocol Sections 5.1 and 5.2](#)), participants will be randomly assigned in a 1:1:1 ratio to 1 of the cohorts 1, 2 or 3. Once recruitment to first three cohorts is completed all participants will enrol cohort 4:

[figure not shown]
- **Cohort 1:** 1.6×10^{11} total cells of EDP1815 or matching placebo administered as 2 capsules once daily.
- **Cohort 2:** 6.4×10^{11} total cells of EDP1815 or matching placebo administered as 2 capsules once daily.
- **Cohort 3:** 6.4×10^{11} total cells of EDP1815 or matching placebo administered as 1 capsule of 3.2×10^{11} cells twice daily.
- **Cohort 4:** 8.0×10^{10} total cells of EDP1815 or matching placebo administered as 1 capsule once daily.

Participants in Cohorts 1, 2, & 3 will be randomised in a 3:1 ratio (approximately 75 to EDP1815 and 25 to placebo within each cohort, 300 in total). Participants in Cohort 4 will be randomised in a 2:1

ratio (approximately 70 to EDP1815: 35 to placebo, 105 in total). So approximately 405 participants will be randomised in total.

As shown in Figure 1, the study comprises a screening period of up to 4 weeks, a treatment period of 16 weeks, and a 4-week post-treatment follow-up period, which results in a maximum study duration of up to 24 weeks. Should a participant elect to participate in an Open Label Extension (OLE) protocol for EDP1815, the follow-up period will be skipped, and the study duration would be a maximum of 20 weeks.

Figure 1 Study Schema

An interim analysis may be undertaken prior to the end of recruitment in cohorts 1-3. The purpose of this interim analysis is to check that the treatment groups have remained balanced and that the use of stratified randomisation has not led to issues caused by multiple incomplete blocks of randomisation. A separate interim analysis process plan is available which provides all relevant details.

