7.1.2.5 Efficacy Data Point Set 5 (EDPS5)

EDPS5 is a subset of EDPS1 for the EASI-50 response data only, excluding any data collected or imputed after the unblinding of a participant or other protocol deviations affecting efficacy (whichever occurs first) and excluding all data from subjects who take <75% of expected doses ([Section 5.3.2.1](#)) or whose compliance with emollient use was <75% ([Section 5.3.2.2](#)).

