6 Summary of Changes from the Protocol..... 11

7 Bibliography 11

8 Appendix 1: List of Tables, Figures and Listings 12

 8.1 Efficacy 12

 8.1.1 Tables 12

 8.1.2 Figures..... 12

9 Appendix 2: List of [name] patients..... 13

Table of Tables

Table 1: Summary of Changes from the Protocol and the main SAP 11

2 Abbreviations and Definitions

BSA	Body Surface Area
BMI	Body Mass Index
CI	Confidence Intervals
DPS	Data Point Set
EASI	Eczema Area and Severity Index
FAS	Full Analysis Set
PS	Propensity Score
SD	Standard Deviation
SAP	Statistical Analysis Plan
vIGA	Validated Investigator Global Assessment

3 Introduction

The purpose of this SAP Cohort 4 Addendum is to provide information that, together with the main SAP, is necessary to perform the required cohort 4 specific statistical analyses of study EDP1815-207. It also defines the cohort 4 specific TFLs to be included in the final clinical study report according to the protocol. The SAP addendum is based upon, and assumes familiarity, with the study protocol, version 5.0, dated 25-Apr-2022.

Only additional information specific to cohort 4 analyses or different from what was stated in the main SAP is included in this SAP addendum. The main study SAP should be referred to for all derivations, estimand definitions and model specifications.

Changes to the analyses described in the protocol or the main SAP other than those already listed in the main SAP are summarised in Section 0.

If a future protocol amendment necessitates a substantial change to the statistical analysis of the study data, this SAP Addendum will be amended accordingly. The content of this SAP Addendum is compatible with the ICH E9 Guidance document.

4 Efficacy Analyses

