4.3 Primary Efficacy Analysis

For all estimands intercurrent events will be accounted for as described in the main SAP.

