4.3.2 Main Analytical Approach

The primary analysis will be performed using a logistic regression model as described in the main SAP.

Treatment will consist of 4 levels (cohort 4 placebo, matched placebo from cohorts 1-3, cohort 4 EDP1815 and cohort 1 EDP1815). Baseline vIGA will consist of 3 levels (2, 3 and 4).

The following treatment differences will be of estimated:

- Cohort 4 EDP1815 vs Cohort 4 matched placebo
- Cohort 4 EDP1815 vs Cohort 1 EDP1815*
- Cohort 4 EDP1815 vs Cohort 4 placebo**

* Comparisons between cohort 4 EDP1815 and cohort 1 EDP1815 will be considered as exploratory analysis.

** Comparisons between cohort 4 EDP1815 and cohort 4 placebo will be considered as sensitivity analysis.

P-values will be only displayed for the comparison of active treatment vs placebo groups.

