8.1 Efficacy

All efficacy outputs numbers will be displayed as 14.2.xx.xx.xxB to distinguish from cohorts 1-3 analysis outputs.

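### The study drug compliance formula assumes 2 capsules per day and has no Cohort 4 rule, so a fully adherent Cohort 4 participant scores 50% and drops out of EDPS5

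*SAP*

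**What the plan says.** SAP 5.3.2.1 (Study Drug Compliance) begins "Participants in cohorts 1 and 2 will be expected to dose once daily with 2 capsules per dose (2 capsules per day" and goes on to Cohort 3, also 2 capsules per day, taken as 1 capsule twice daily. Cohort 4 is not mentioned. The section then defines, for all participants:

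- expected capsules = 2 × (date of last dose − Day 1 + 1);
- capsules not taken by accountability = expected − (dispensed − returned);
- actual capsules = expected − the larger of the diary count and the accountability count of capsules not taken;
- compliance = 100 × actual / expected, split at 75%.

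The Cohort 4 regimen is given elsewhere. Protocol Table 6-1 has "1 capsule, once daily", and SAP 5.1 describes Cohort 4 as a number of "total cells of EDP1815 or matching placebo administered as 1 capsule once daily".

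SAP 7.1.2.5 uses the compliance figure to define EDPS5, "excluding all data from subjects who take <75% of expected doses", with a cross-reference to 5.3.2.1. EDPS5 corresponds to supplementary estimand 4.

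The Cohort 4 Addendum gives no compliance rule of its own. Its Introduction says "The main study SAP should be referred to for all derivations, estimand definitions and model specifications", and its Section 4.3 says "For all estimands intercurrent events will be accounted for as described in the main SAP".

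**The concern.** The multiplier 2 is correct for the three cohorts named and twice too large for the fourth. Because the formula takes the larger of the two counts of missed capsules, the accountability count treats half of a perfect Cohort 4 record as missed doses.

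What is at stake is the analysis restricted to compliant participants in Cohort 4. Protocol 11.3.1 applies the supplementary estimands to Cohort 4, and SAP 9.3 says Cohort 4 follows the same approach as Cohorts 1 to 3. The Addendum lists only additional outputs and renumbers the rest: "All efficacy outputs numbers will be displayed as 14.2.xx.xx.xxB to distinguish from cohorts 1-3 analysis outputs". So the EDPS5 tables are planned for Cohort 4.

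The damage is lopsided. Addendum 4.3.2 states "Treatment will consist of 4 levels (cohort 4 placebo, matched placebo from cohorts 1-3, cohort 4 EDP1815 and cohort 1 EDP1815". Two of those four groups come from Cohorts 1 to 3, are scored correctly and stay in. The two Cohort 4 groups are the ones removed.

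**Working it through.** **Inputs**

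- Capsules per day: Cohort 1, 2 × 1 = 2; Cohort 2, 2 × 1 = 2; Cohort 3, 1 × 2 = 2; Cohort 4, 1 × 1 = 1 (Protocol Table 6-1).
- Treatment length D = 112 days (16 weeks, SAP 10.1).
- Cut-off 75% (SAP 5.3.2.1 and 7.1.2.5).
- Cohort 4 size: 70 EDP1815 and 35 placebo (SAP 5.1); planned drop-out 20% (SAP 6).

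**Formula**, with k the capsules per day in the expected count:

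E = k × D; compliance = 100 × [E − max(diary missed, E − (dispensed − returned))] / E.

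**Reproducing the plan for Cohorts 1 to 3.** Adherent and reconciled: E = 2 × 112 = 224, dispensed − returned = 224, not taken = max(0, 0) = 0, compliance 224/224 = 100.0%. The formula works for the cohorts it names.

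**Cohort 4, 112 days**

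| Participant | k = 2 (as written) | k = 1 (own regimen) |
|---|---|---|
| Every capsule taken, reconciled | E = 224; not taken max(0, 224 − 112) = 112; 112/224 = **50.0%** | E = 112; not taken 0; 112/112 = **100.0%** |
| 14 missed (98 taken) | 98/224 = 43.75% | 98/112 = 87.5% |
| 28 missed (84 taken) | 84/224 = 37.5% | 84/112 = 75.0% (kept) |
| 29 missed (83 taken) | 83/224 = 37.1% | 83/112 = 74.1% (excluded) |

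For an adherent, reconciled participant the as-written result is D/(2D) = 50.0% at any treatment length.

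**What it takes to reach 75% as written.** Dispensed − returned must be at least 0.75 × 2D = 1.5D. An adherent participant has taken D, so at least D/2 capsules must be unaccounted for. Over 112 days that is 168 − 112 = 56 (167/224 = 74.6%; 168/224 = 75.0%).

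Protocol 6.3 puts 30 capsules in a carton, and Protocol 7.2 to 7.5 describe four dispensings, each meant as a 4-week supply. The number of cartons per dispensing is not stated. If it is one for Cohort 4 (an assumption), 120 capsules are dispensed in all, and even with none returned compliance over 112 days is at most 120/224 = 53.6%.

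**How many are affected.** Completers at 20% drop-out: 70 × 0.8 = 56 active and 35 × 0.8 = 28 placebo, 84 of 105 in total. Over an assumed range, 10% drop-out gives 94.5 and 25% gives 78.75.

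**The case against.** The strongest reply is that the opening sentence confines the formula to Cohorts 1 to 3, so the SAP says nothing about Cohort 4 compliance instead of getting it wrong. That reading is possible, but it does not help: Cohort 4 compliance and EDPS5 membership would then be undefined, although Cohort 4 columns and outputs are planned. The same correction is needed.

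Second, the 50% arises only through the accountability count. From the diary alone an adherent participant scores 100%. This is right, and it is why the result is stated for reconciled participants. But the SAP takes the larger count of missed capsules, so accountability governs whenever it is available.

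Third, 84 is not an EDPS5 denominator from the documents. The SAP version of EDPS5 has no completion requirement, so participants who stop early face the same filter, and the number excluded could approach 105. Some early stoppers who return few capsules could still pass. The figure is an illustration.

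Fourth, the effect is limited and would be easy to notice, since Cohort 4 compliance near 50% would stand beside correct figures for the other cohorts. This stands as a limit on severity. It does not remove the need for a rule: a programmer who corrected it would be departing from the SAP on who is analysed, without documentation.

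One point on scope also stands. SAP 10.1 summarises doses taken and lists capsules taken without saying how they are derived. If they reuse the actual capsule count of 5.3.2.1, a reconciled participant is counted correctly (112), but one with no accountability data would show 224 − 0 = 224.

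**Conclusion.** The concern holds. As written, SAP 5.3.2.1 gives 50.0% compliance to a Cohort 4 participant who is fully adherent and whose supplies are reconciled, and EDPS5 then excludes that participant. For Cohort 4, supplementary estimand 4 would keep the borrowed placebos and Cohort 1 EDP1815 and lose nearly all adherent completers in the active and concurrent placebo arms. The comparison of Cohort 4 EDP1815 with its matched placebo group could not be meaningfully estimated. The Cohort 4 columns of Table 14.1.5 and the Cohort 4 entries in Listing 16.2.5.2 would show about 50% for adherent participants.

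This rests on applying the formula literally, on accountability data being available, and on no Cohort 4 rule existing outside the readable text. Neither table of changes (SAP 13, Addendum 6) mentions one. Addendum 4.3.3.3 is redacted, but its title and outputs show it to be a subgroup analysis.

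The primary estimand (EDPS1, treatment policy for non-compliance) and the secondary efficacy analyses do not use the compliance figure. Nor do the safety analyses, apart from the exposure question about SAP 10.1 noted above. It should be fixed, but it does not threaten the main result.

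**What to change.** In SAP 5.3.2.1, or in the Addendum, define expected capsules = k × (end date − start date + 1), with k the capsules per day already given in Protocol Table 6-1: 2 for Cohorts 1 to 3 and 1 for Cohort 4. Use this definition for EDPS5, Table 14.1.5 and Listing 16.2.5.2. State whether the capsule counts in SAP 10.1 come from the same derivation. Record the change in the Addendum's table of changes before Cohort 4 is unblinded.

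The cost is one line of text and one programming parameter. No new data are needed, and nothing changes for Cohorts 1 to 3.

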5.3.2.2 Emollient Compliance

All participants must use an emollient twice daily for at least 14 consecutive days immediately prior to randomisation and should continue the background emollient treatment twice daily until the the end of the study.

Compliance will be calculated across the whole treatment period.

Expected number of applications for the treatment period will be calculated as:

Expected number of applications = $2 \times (\text{End date of period} - \text{Start date of period} + 1)$.

End date of period = End of study treatment day.

Start date of period = Day 1.

Actual number of applications will be calculated from the emollient usage diary using entries between the start and end days inclusively. In case of more than two applications per day participant will be considered compliant for that day and only two applications will be considered for compliance calculation.

Emollient compliance will be calculated as:

Emollient compliance (%) = $100 \times \text{Actual number of applications} / \text{Expected number of applications}$.

Emollient compliance will also be categorised as:

- <75%
- $\geq 75\%$

5.3.2.3 Prohibited Concomitant Medications

The following medications are not allowed at any point during the study:

- Live (attenuated) vaccinations (a non-replicating / non-live vaccine when the first dose of IMP was not taken within a 7-day window of the administration of vaccine is allowed).

Type 1 prohibited medications are prohibited concomitant medications which may affect efficacy requiring the concomitant medication to be immediately discontinued where possible once the use is discovered. If the prohibited medication cannot be discontinued for any reason, then the IMP should be discontinued:

- Emollients containing additives including SLS.
- Topical Corticosteroids (TCS) or Topical Calcineurin Inhibitors (TCI) (unless considered a rescue therapy).
- Topical PDE-4 Inhibitors.
- Bleach baths.
- Tanning beds.
- Leukotriene Receptor Antagonists.
- Allergen Immunotherapy.

Type 2 prohibited medications are prohibited concomitant medications which may affect efficacy requiring IMP discontinuation:

- Phototherapy treatment
- Systemic treatments that may lead to clinical improvements in atopic dermatitis, e.g., oral or injectable corticosteroids, methotrexate, azathioprine, cyclosporine, mycophenolate mofetil, JAK-inhibitors, biologic therapy, and other systemic immunosuppressive therapy (note single dose intra-articular or intra-lesional corticosteroid therapy is permitted).

If a prohibited medication is found to have been used, this will be captured into the protocol deviations log.

Prohibited medications will be identified by the sponsor in a separate spreadsheet.

Any medications taken during the study and classified as type 1 prohibited medications in the spreadsheet will be considered as type 1 prohibited medications with exception for

1. Medications which stopped at least 14 days before Day 1
2. Medications which started strictly before screening and carried on throughout study to week 16
3. Medications which are emollients and started on or after screening, but before Day 1
4. Medications which are emollients and started before screening and stopped before Day 1

Any medications taken during the study and classified as type 2 prohibited medications in the spreadsheet will be considered as type 2 prohibited medications with exception for medications which stopped at least 14 days before Day 1.

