5.2. Exclusion criteria

Participants are not permitted to enroll in the study if any of the following criteria is met:

1. Atopic dermatitis limited to the hands and/or feet and/or scalp.
2. Have been in a clinical trial for EDP1815 prior to signing of ICF.
3. History of active skin infection within 14 days prior to randomization.
4. Evidence of dermatologic conditions that may, in the opinion of the investigator, interfere with AD evaluation or the assessment of treatment response.
5. Use of phototherapy or tanning beds; systemic medications/treatments that could affect AD or its symptoms including immunosuppressive therapy (e.g., oral or injectable corticosteroids, methotrexate, azathioprine, cyclosporine, mycophenolate mofetil, JAK inhibitors, tacrolimus, and/or leukotriene inhibitor) within 4 weeks of randomization.
6. Previously received any biologic agent for AD and either was:
 - a. Unresponsive to biologic agent, or
 - b. Responsive to biologic agent and received this therapy within 3 months or 5 half-lives prior to randomization, whichever is longer.
7. Treatment with topical agents that could affect atopic dermatitis, including topical corticosteroids, topical calcineurin inhibitors (e.g., tacrolimus or pimecrolimus), or topical PDE-4 inhibitor (e.g., crisaborole) within 14 days prior to randomization.
8. Received any investigational or licensed biologic agent for conditions other than AD:
 - a. Any cell-depleting agent, including rituximab, within 6 months prior to randomization, or until lymphocyte cell counts return to normal, whichever is longer.
 - b. Any other biologic agent, within 3 months or 5 half-lives prior to randomization, whichever is longer.
9. Gastrointestinal tract disease (e.g., short-bowel syndrome, diarrhea-predominant irritable bowel syndrome) that could interfere with GI delivery and transit time.
10. Active inflammatory bowel disease.
11. Ongoing acute or chronic infectious disease. Patients with hepatitis B, hepatitis C, and HIV may be enrolled provided that the disease is adequately controlled and/or is in remission.
12. Has received live or live-attenuated vaccination within 6 weeks prior to Screening or intends to have such a vaccination during the study. Non-live and non-replicating vaccines are permitted.

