5.3.3.14 Rescue Therapy

Rescue therapy use is allowed throughout the entire study: selected topical corticosteroids and calcineurin inhibitors systemic antimicrobials and topical antibacterial may be prescribed. An unscheduled visit will be performed to collect skin assessments prior to administering any rescue therapy, if needed.

Rescue therapy use will be documented as concomitant medication once prescribed and in a daily symptom diary during the whole course. Each rescue therapy course will be recorded in concomitant medication CRF separately, resulting in a one record in a concomitant medication dataset for each course.

Any medications taken during the study and classified as TCS/TCl rescue therapy medications in the sponsor provided spreadsheet with total course duration no more than 8 days (adjusted for dosing

frequency – only days with planned medication usage are counted in course duration) will be considered as rescue therapy with exception for medications which stopped at least 14 days before Day 1 – these cannot be rescue therapy.

For the number of courses of TCS/TCI rescue therapy in Weeks 1-4, 5-8, 9-12, 13-16, course will only be counted at the start day of course. If the rescue therapy course starts in one period and continues to the next period it will be counted only in the first period where the start of the course belongs. The number of courses of rescue therapy will be also evaluated for the whole period of Weeks 1-16.

For the same periods, rescue therapy use will be evaluated. In case of rescue therapy course overlap with the period, the participant will be considered as those who used rescue therapy in this period.

The number of days requiring TCS/TCI rescue therapy in Weeks 1-8, 9-16, 1-16 will be calculated as:

Number of days requiring rescue therapy (days) = min(therapy stop date, the end of the period date) – max(therapy start date, the start of the period date) + 1

In case of multiple rescue therapy medications concurrently, the day still will be counted only once.

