7.1.2.1 Efficacy Data Point Set 1 (EDPS1)

EDPS1 consists of all data collected at a scheduled timepoint that is at least 28 days after use of TCS/TCI rescue therapy* or type 1 prohibited medication and before use of type 2 prohibited medication. Data collected less than 28 days after such use or data missing due to withdrawal from the study for reasons considered related to study medication** or data collected after use of type 2 prohibited medications will be replaced as follows:

- Continuous endpoints: value will be imputed with the last off-rescue¹ observation in the period before the event plus early termination visit in case of early study discontinuation (off-rescue is defined as data collected at least 28 days after use of rescue medication or type 1 prohibited medication)
- Responder endpoints: value will be imputed as non-response.
- Count endpoints: N/A (no count endpoint will use this DPS).

Data missing for other reasons, including early withdrawal from the study due to reasons not considered related to study medication will not be replaced and will be considered as missing.

Example 1: if patient completed 16 weeks of study with rescue therapy during week 3 and then during week 10 then responder endpoints will be analysed as shown in table:

Week 0	Week 2	Week 4	Week 8	Week 12	Week 16
As collected	As collected	Imputed as non-responder because there was a rescue therapy within 28 days before Week 4 visit	As collected	Imputed as non-responder because there was a rescue therapy within 28 days before Week 12 visit	As collected

Example 2: if patient completed 16 weeks of study with rescue therapy from Day 25 to Day 31 then responder endpoints will be analysed as shown in table:

Week 0	Week 2	Week 4	Week 8	Week 12	Week 16
As collected	As collected	Imputed as non-responder because there was a rescue therapy within 28 days before Week 4 visit	Imputed as non-responder because there was a rescue therapy within 28 days before Week 4 visit	As collected	As collected

Example 3: if patient withdrew study early due to the lack of efficacy after 12 weeks of treatment with rescue therapy during week 3 (unscheduled rescue therapy visit was not done) and then during week 10 (unscheduled rescue therapy visit was done at Week 9 prior to the rescue therapy start) then continuous endpoints will be analysed as shown in table:

Week 0	Week 2	Week 4	Week 8	Week 12	Week 16

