7.1.2.6 Efficacy Data Point Set 6 (EDPS6)

EDPS6 consists of data collected in the absence of TCS/TCI rescue therapy* and type 1 prohibited medication at any time since Day 1 for the responder endpoints relating to EASI, vIGA and PP-NRS. Data collected after such use will be imputed as non-response. Data missing due to withdrawal from the study for reasons considered related to study medication** and data after use of type 2 prohibited medication will be imputed as per EDPS1.

Responses missing for other reasons, including early withdrawal from the study due to reasons not considered related to study medication will not be replaced and will be considered as missing.

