9.3.1 Primary Efficacy Estimand

The primary efficacy estimand will be the effect of each individual EDP1815 cohort compared to the pooled placebo group on the percentage of participants achieving EASI-50 at Week 16. The population summary measure of interest will be the odds ratio between each active EDP1815 treatment group and pooled placebo.

Intercurrent events will be accounted for in the following manner:

Table 1 Intercurrent Event Strategies for the Primary Estimand (EDPS1)

Intercurrent event		
Use* of Permitted TCS/TCI Therapy or Type 1 Prohibited Medications ¹	Study Discontinuation Before Week 16 Visit or Type 2 Prohibited Medications ² Use	Noncompliance or Unblinding or Other Protocol Deviations Affecting Efficacy Before Week 16

If <28 days before Week 16 visit: Composite strategy Participant will be considered a non-responder
 
If ≥28 days before Week 16 visit: Treatment policy strategy Data will be used as collected
	
If type 2 prohibited medication² used: Composite strategy Participant will be considered a non-responder from the date of medication start
 
If due to related** reason: Composite strategy Participant will be considered a non-responder from the time of treatment discontinuation in case of missing data
 
If due to non-related** reason: While-on-treatment strategy No replacement of missing data (data after treatment discontinuation will be used as collected)
	
Treatment policy strategy: Data will be used as collected

* Consider the last day with therapy for participant before Week 16.

** Treatment discontinuation reasons will be checked. Reasons related to study medication are lack of efficacy, treatment failure, adverse event (if related). Also, withdrawal of consent may be considered related to study medication based on the clarification text provided, that will be assessed by the Evelo team and provided in a separate spreadsheet. Non-related reasons are all other reasons.

¹Prohibited concomitant medications which may affect efficacy requiring the concomitant medication to be immediately discontinued where possible once the use is discovered. Such medications use will be recorded as protocol deviation. Classification will be provided by the sponsor in a separate spreadsheet.

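### SAP 5.3.2.3 exemption 2 has no drug-class limit, so a barred topical steroid that is never stopped is accepted at Week 16, while one stopped the day before is scored as non-response

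*SAP*

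**What the plan says.** **Definition.** The type 1 list in SAP 5.3.2.3 has an entry beginning "Topical Corticosteroids (TCS) or Topical Calcineurin Inhibitors (TCI) (unless considered a rescue therapy", and a separate entry for topical PDE-4 inhibitors. The operative rule reads "Any medications taken during the study and classified as type 1 prohibited medications in the spreadsheet will be considered as type 1 prohibited medications with" four listed exceptions. The second is "Medications which started strictly before screening and carried on throughout study to week 16". The third and fourth are expressly confined to emollients; the second is not confined to anything. The parallel rule for type 2 drugs has only one exception, for drugs stopped at least 14 days before Day 1.

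**Use of the definition.** EDPS1 (SAP 7.1.2.1) keeps data collected "at least 28 days after use of TCS/TCI rescue therapy* or type 1 prohibited medication". For use inside 28 days of Week 16, Table 1 in SAP 9.3.1 says "Participant will be considered a non-responder". EDPS6 (SAP 7.1.2.6) keeps responder data collected "in the absence of TCS/TCI rescue therapy* and type 1 prohibited medication at any time since Day 1". The Cohort 4 addendum (4.3) adopts the same intercurrent-event handling.

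**Entry.** Protocol 5.2, criterion 7, excludes "Treatment with topical agents that could affect atopic dermatitis, including topical corticosteroids, topical calcineurin inhibitors" and topical PDE-4 inhibitors within 14 days before randomisation.

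**Purpose.** The primary objective in SAP 4.1 asks for EASI-50 with no rescue for 28 days and no prohibited drug at any point. SAP 13 explains that prohibited drugs were given their own strategies because they could influence efficacy. It does not mention the exemption.

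**The concern.** The type 1 rule exists to stop active eczema treatment from being counted as an EDP1815 or placebo response. Exemption 2 lifts the rule for the one pattern in which such treatment is certain to be in use at the Week 16 assessment. For the three topical classes, that pattern is an entry violation rather than permitted background therapy. At stake is how some primary-endpoint values are classified, and whether EDPS6, the strictest rescue analysis, is as strict as its wording suggests.

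**Working it through.** **1. Rule trace.** Take a non-rescue topical steroid started before screening, with Week 16 on nominal Day 113 (Protocol Table 4-1). Days before the visit = 113 − last day of use.

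| Last day of use | Days before visit | Exempt? | EDPS1 | EDPS6 |
|---|---|---|---|---|
| 85 | 113 − 85 = 28 | no | as collected | non-response |
| 86 | 27 | no | non-response | non-response |
| 100 | 13 | no | non-response | non-response |
| 112 | 1 | no | non-response | non-response |
| still in use at 113 | 0 | yes, exemption 2 | as collected | as collected |

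The penalty applies as use approaches the visit and vanishes when use reaches it. EDPS2, EDPS3 and EDPS4 rest on the same type 1 definition and inherit the gap.

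**2. Does another rule catch the case?**
- *Rescue.* SAP 5.3.3.14 requires a TCS/TCI course "with total course duration no more than 8 days", counting only planned-use days. Day 1 to Day 113 is 113 days, and 113 / 8 ≈ 14, so only a drug planned about once a fortnight or less could fit. PDE-4 inhibitors are not TCS/TCI.
- *Type 2.* That list covers phototherapy and systemic treatments, not topicals.
- *Other deviations affecting efficacy.* Table 1 uses treatment policy, so the value stands as collected.
- *Analysis population.* All randomised participants are included (SAP 7.1.1.2), so an entry violator stays in.
- *EDPS5.* It drops data after other deviations affecting efficacy. It would exclude the case only if the deviation is so classed, which the SAP does not state.

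**3. Scale (illustration only).** The documents give no count of exempt users. The planning inputs in SAP 6 are 25% vs 50%, two-sided 5%, 80% power. With pooled variance under the null:

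n = [1.960·√(2·0.375·0.625) + 0.842·√(0.1875 + 0.25)]² / 0.25² = 57.7, so 58 per group; 58 / 0.8 = 72.5, so 73.

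Both match the plan, and neither is affected by this point.

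*Equal shares.* Suppose a share f of each arm is exempt and responds at rate r, the others responding at 25% and 50%. As collected, p = (1 − f)·p₀ + f·r; if scored as non-response, p = (1 − f)·p₀. With r = 0.75 (assumed):

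| f (assumed) | As collected: placebo / active, OR | As non-response: placebo / active, OR |
|---|---|---|
| 1% | 25.5% / 50.25%, 2.95 | 24.75% / 49.5%, 2.98 |
| 5% | 27.5% / 51.25%, 2.77 | 23.75% / 47.5%, 2.90 |
| 10% | 30.0% / 52.5%, 2.58 | 22.5% / 45.0%, 2.82 |

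*One arm only.* With 58 per arm and base OR (29/29) / (14.5/43.5) = 3.00, reclassifying one exempt active responder gives (28/30) / (14.5/43.5) = 2.80, and three give 2.44. Reclassifying one exempt placebo responder gives (29/29) / (13.5/44.5) = 3.30, and three give 4.04. The sign depends on the arm in which the responders fall.

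**The case against.** **Stable use is already in the baseline.** Baseline is the last pre-dose value (SAP 5.3.1.2), so an exempt user's baseline was taken on the drug. That user still had to show vIGA 2 to 4, BSA of at least 5% and EASI of at least 6 at Screening and Day 1, and then needs a further 50% fall. This stands as a limit on the harm: heavy exposure at Week 16 is not the same as bias in change from baseline. It does not justify the rule. The SAP never gives this reason, and the participant should not have been randomised under exclusion 7.

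**The data sets are formally consistent.** EDPS1 and EDPS6 use the defined term, and the definition includes its exceptions. That is correct. The real conflict is with SAP 4.1, which refers to prohibited drugs at any time. SAP 4.1 is already stricter than Table 1, because type 1 use ending 28 or more days before Week 16 is accepted; exemption 2 widens that gap.

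**The protocol used treatment policy.** Protocol Table 11-1 did so for prohibited medication. SAP 13 deliberately replaced that, and the exemption restores it for one subgroup without saying so.

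**Safeguards make cases rare.** Entry screening, concomitant-medication review, the instruction that the drug or else IMP be stopped (Protocol 6.9.2.2) and the deviation log all stand in the way. Small numbers are likely, though none are given.

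**Stronger readings that a reader might infer, and that the documents do not support:**
- *That exempt users are more common on placebo and so dilute the effect.* Use must start before screening, so its start cannot depend on arm. Only persistence could differ, and nothing in the documents suggests that it does.
- *That each exempt user switches a responder.* A value changes only if that user reached EASI-50.
- *That one or two such users would overturn significance.* Any such example rests on freely chosen counts and a chosen arm.

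**Conclusion.** The point holds as a flaw in a stated rule. For TCS, TCI and topical PDE-4 inhibitors, exemption 2 makes the primary estimand non-monotone in exposure, carries the gap into EDPS6, and contradicts the SAP's own objective and its reason for the type 1 rule. This follows from the text and needs no assumption about frequency. The numerical effect is unknown. Under the illustrative equal shares of 1% to 10% with 75% response, the odds ratio moves by 0.03 to 0.24; with one to three exempt responders in a single arm it can move either way. The documents do not support a claim that the trial is biased in a given direction or that its conclusion would change. The change should be made because the classification is wrong on its face and cheap to correct.

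**What to change.** This concerns analysis classification only; it changes no treatment rule and no sample size.

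1. In SAP 5.3.2.3, state that exemption 2 does not apply to TCS, TCI or topical PDE-4 inhibitors, so that use less than 28 days before a visit counts as type 1 whatever the start date.
2. Name the classes to which exemption 2 does apply, with the reason for each. Not being barred at entry is not a safe shorthand. Emollients with additives are barred by inclusion 5 and Protocol 6.9.1.1, and exclusion 5 also names tanning beds and leukotriene inhibitors. Of the type 1 entries, only bleach baths and allergen immunotherapy are not named in the entry criteria.
3. Reconcile SAP 4.1, 5.3.2.3, 7.1.2.6 and Table 1 in 9.3.1, and record the exemption in SAP 13.
4. If the classification has already been applied, report the number of exempt users by arm and add a sensitivity analysis scoring them as non-responders.

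The cost is a line or two of SAP text and an update of the sponsor's classification spreadsheet.
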